- MDS-UPDRS part III changes from OFF medication baseline at 28 and 54 weeks
- Non-Motor Symptoms Scale (NMSS) changes from ON medication baseline at 28 and 54 weeks

- PDQ-39 Quality of Life scale changes from baseline at 28 and 54 weeks
- MDRS-2 changes from ON medication baseline at 28 and 54 weeks. This test assesses overall cognitive functioning on 5 subscales measuring specific abilities including attention, initiation/perseveration, construction, conceptualization, and memory.
- To complement the MDRS-2, additional neuropsychological assessment tools will include:
 - Delis-Kaplan Executive Function System (DKEFS) Verbal Fluency, a standardized assessment tool with robust psychometric properties. Verbal fluency has been established as a highly sensitive cognitive construct to neuropathology in individuals with PD (e.g., sensitive to striatal pathology or dorsolateral frontal dysfunction).
 - Geriatric Depression Scale
 - The Parkinson's Anxiety Scale.
 Inclusion of these brief mood measures will assist in assessing drug effects on the subjects' health-related quality of life.

Assessments for Safety: Safety and tolerability will be assessed by changes in vital signs, weight, clinical laboratory measures, and adverse events. Routine laboratory studies performed at the beginning and the end of the study will include CBC, renal function, liver function, serum amylase, serum lipase, serum calcitonin⁷⁷, and fasting serum glucose and insulin. In addition, an ECG will be performed at baseline and follow-up visits. The number of patients completing the study will be calculated and will establish the tolerability of the study compound at the studied doses. It is expected that over 80% (43 subjects) will safely complete the study.

Other Assessments: Measures of peripheral insulin sensitivity will be used to test the association of changes in such sensitivity to changes in MDS-UPDRS and MDRS-2 scores from baseline to 28 and 54 weeks. Surrogate measures of peripheral insulin sensitivity will be used, specifically the homeostasis model assessment of insulin resistance (HOMA-IR) and the quantitative insulin sensitivity check index (QUICKI).^{61,62} HOMA-IR is defined as fasting glucose (mmol/L) × fasting insulin (mU/L)/22.5. QUICKI is defined as $1/[\log \text{fasting insulin (mU/L)} + \log \text{fasting glucose (mg/dL)}]$.

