Sample Size Calculation: This is a randomized, double-blinded, placebo-controlled clinical trial that aims to evaluate the effects of liraglutide on motor and non-motor symptoms in patients diagnosed with PD. The primary outcome of this study will be the difference in MDRS-2 scores at baseline and follow-up (52 weeks after titration) between the active and placebo control group. The power analysis was performed utilizing data reported in a previous study using a similar GLP-1 agonist (**Table 1**). While score changes associated with active medication were not compared to a placebo group but to a cohort of patients treated with “conventional PD medication”, this data represent the closest approximation available for power analysis and sample size calculation.

With a total of 57 patients (38 in the drug group and 19 in the placebo group), the study will have an 82.7% chance of rejecting the null hypothesis of equal means, assuming an average critical difference of 5.1 points on the MDRS-2 and a standard deviation of 6.4 for the drug group and 5.3 for the placebo group with a significance level (alpha) of 0.050 using a two-sided two-sample unequal-variance t-test.

This sample allows for a 12% dropout of up to 6 subjects (e.g., if they are diagnosed with T2D during the course of the study) and still maintain 81.3% power with a total of 51 patients (i.e., 36 cases in the drug group and 15 cases in the placebo group). If the rate of drop out is higher than anticipated, the study will enroll and randomize additional subjects; subjects will be enrolled/randomized in multiples of 3 subjects in order to maintain the 2:1 randomization. The additional enrolled subjects will aim to maintain the power of the study. In total, up to 63 patients will be enrolled and randomized. No more than 42 patients, including drop outs, will be exposed to the drug during the trial.

Statistical Methods: The analysis populations for this study are defined as:

1. Full Analysis Set (FAS): all randomized subjects who receive at least one dose of study drug and have a baseline and at least one post-baseline efficacy score (MDRS-2 and MDS-UPDRS).
2. Per-Protocol (PP) population: a subset of the FAS population, excluding subjects with major deviations from the protocol that may substantially affect the results of the primary efficacy analysis.
3. Safety population: all randomized subjects who receive at least one dose of study drug.

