4 weeks after the end of the study, a phone interview will be completed to assess adverse events which were ongoing at the end visit (Week 54) and concomitant medications.

Post-study follow-up (6 month)

26 weeks after completing the active phase of the study (end visit), subjects originally assigned to both treatment arms will undergo a follow-up visit including MDS-UPDRS OFF and ON testing and neuropsychological testing (ON) in addition to an assessment of adverse events which were ongoing at the end visit (Week 54), concomitant medications, routine vitals, an ECG, and blood and urine tests. At this stage, enrolled subjects will no longer be on study treatment. However, the study team may continue to follow subjects who opt to continue liraglutide off-label.

Post-study follow up (12 month)

52 weeks after completing the active phase of the study (end visit), subjects originally assigned to both treatment arms will undergo a follow-up visit including MDS-UPDRS OFF and ON testing and neuropsychological testing (ON) in addition to an assessment of adverse events which were ongoing at the end visit (Week 54), concomitant medications, routine vitals, an ECG, and blood and urine tests. At this stage, enrolled subjects will no longer be on study treatment. However, the study team may continue to follow subjects who opt to continue liraglutide off-label.

STUDY DRUGS AND MATERIALS:

Study Medications: Liraglutide 6 mg/ml (Novo Nordisk A/S) will be self-administered subcutaneously once daily at a maximum dose of 1.8 mg after a 2 week titration schedule. Placebo will be administered according to the same schedule (Table 2). At baseline, subjects will be dispensed drug pens preset to deliver 0.6 mg of either liraglutide or vehicle per daily dose. At week 1 visit, after being assessed for tolerability by the investigator, subjects will be titrated to 1.2 mg of either liraglutide or vehicle per daily dose. The same procedure will be repeated at week 2, when subjects will be titrated to 1.8 mg of either liraglutide or vehicle per daily dose, as tolerated. A subject that cannot tolerate at least a 1.2 mg dose will be excluded from the study. Subjects that cannot tolerate the 1.8 mg dose, will be offered to continue at the 1.2 mg dose. The project will include a washout period at study end.

Table 2

Week	Titration Schedule	
	Drug Group	Placebo Group
	Liraglutide Dose	Vehicle Dose
Baseline	0.6 mg	0.6 mg
Week 1	1.2 mg	1.2 mg

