PREMATURE TERMINATION OF STUDY: In case the study is terminated early due to the discovery of an unexpected, significant, or unacceptable risk/safety concern, regardless of how far along the subject has reached in their study follow-up, subjects will be asked to return all unutilized pens to the PI. The study site will then return investigational drug to the drug manufacturer (See also Study Drug Accountability).

PUBLICATION PLANS: The intention of the study will be to publish the results of the complete study at conclusion. All information obtained during the conduct of this study will be regarded as confidential but no written permission from the study funding sources is required prior to disclosing any information relative to this study. A formal publication of data collected as a result of the study will be considered a joint publication by all investigators and appropriate personnel. Authorship will be determined by mutual agreement. Submission to the funding source(s) for review and comment will be intended solely to ensure concurrence regarding data, evaluations, and conclusions, and to provide an opportunity to share with them any new or unpublished information of which they may be unaware.

Schedule of events

Procedures	Screening	Baseline	Week 1	Week 2	Week 3	Week 6	Week 14	Week 28	Week 40	Week 54	Week 58	Week 80	Week 108
Day	Within 30 days of baseline	1	8 + 3	(7+3 days from Week 1)	(7+3 days from Week 2)	42 ± 7	98 ± 7	196 ± 7	280 ± 7	378 ± 7	406 ± 7	560 ± 7	756 ± 7
Sign Consent	x												
Demographics	x												
Medical History	x												
Pregnancy Test	x												
Physical and Neuro Exam	x												
EKG	x		x	x		x	x	x	x	x		x	x
Vitals	x	x	x	x		x	x	x	x	x		x	x
Blood and Urine samples¹	x		x	x		x	x	x	x	x		x	x
Blood for Biomarker Analysis	x							x		x		x	x
Review of eligibility		x											
MDS-UPDRS OFF²		x						x		x		x	x
MDS-UPDRS ON		x						x		x		x	x
BDI-II	x												
NMSS		x						x		x		x	x
MDRS-2	x							x		x		x	x
Neuropsych tests		x						x		x		x	x
Treatment Randomization and First Dose		X (0.6) Placebo	X (1.2) Placebo	X (1.8) Placebo									
Drug Administration Training		x	x	x									
Dispense Study Drug		x	x	x		x	x	x	x				

Review Study Drug Compliance			X	X		X	X	X	X	X			
AE Assessment	X	X	X	X	X	X	X	X	X	X	X	X	X
Assessment of Concomitant Medications		X	X	X	X	X	X	X	X	X	X	X	X
Final dosage determination³					X								

1) Lab tests – schedule across study:

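### The number of study completers cannot establish tolerability at the studied doses, and the expected 43 completers are not over 80% of 57

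*Combined protocol and SAP*

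**What the plan says.** Under Assessments for Safety, the protocol first lists the general measures of safety and tolerability: adverse events, laboratory results, weight and vital signs. It then gives completion a specific role: "The number of patients completing the study will be calculated and will establish the tolerability of the study compound at the studied doses". The next sentence sets the benchmark: "It is expected that over 80% (43 subjects) will safely complete the study". Neither sentence mentions arm or dose.

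The Sample Size Calculation section gives the numbers behind it: "With a total of 57 patients (38 in the drug group and 19 in the placebo group"). If dropout is high, more subjects are added: "In total, up to 63 patients will be enrolled and randomized". Exposure is capped: "No more than 42 patients, including drop outs, will be exposed to the drug during the trial". The same section allows for a "dropout of up to 6 subjects (e.g., if they are diagnosed with T2D during the course of the study").

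Under Study Medications, a subject who cannot tolerate 1.2 mg leaves the study, but: "Subjects that cannot tolerate the 1.8 mg dose, will be offered to continue at the 1.2 mg dose". The Schedule of events has a row for "Final dosage determination" at Week 3. Its footnote 3 lets the investigator change the dose after that.

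Statistical Methods assigns all safety outcomes to the Safety population, grouped by the treatment taken. Descriptive statistics promises a disposition summary with reasons for withdrawal. The list of safety outcomes includes neither completion nor discontinuation of study drug.

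**The concern.** The sentence draws a conclusion about a compound at two doses from one number about the study. There are two gaps between the number and the conclusion.

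- **Arm.** A third of the planned subjects receive vehicle. Their completion carries no direct information on how liraglutide is tolerated, yet the benchmark appears to include them.
- **Dose.** Step-down from 1.8 mg to 1.2 mg is part of the regimen. A subject who failed 1.8 mg and finished on 1.2 mg is a completer, and so is one who took 1.8 mg throughout.

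Non-completion also mixes intolerance with other causes, such as a new diabetes diagnosis. That makes the number harder to interpret, although it lowers completion and does not flatter the drug.

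At stake is the tolerability statement in the report. Followed literally, the plan would support a sentence about both doses with a figure that cannot distinguish them and that could look satisfactory while the liraglutide arm did appreciably worse.

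**Working it through.** **Inputs**

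| Quantity | Value | Place |
|---|---|---|
| Planned subjects | 57 = 38 liraglutide + 19 placebo | Sample Size Calculation |
| Maximum randomised | 63; at 2:1, 42 + 21 | Sample Size Calculation |
| Maximum exposed to liraglutide | 42 | Sample Size Calculation |
| Subjects left after the dropout allowance | 57 − 6 = 51 | Sample Size Calculation |
| Expected completers | over 80%, 43 | Assessments for Safety |

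**Step 1. Reproduce the benchmark.** Required count = 0.80 × N, rounded up.

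- N = 57: 0.80 × 57 = 45.6, so 46 are needed. 43/57 = 75.4%.
- N = 63: 0.80 × 63 = 50.4, so 51 are needed. 43/63 = 68.3%.
- N = 51: 43/51 = 84.3%, but 51 is already the number left after dropout.
- N = 53: 0.80 × 53 = 42.4, so 43 would be right, but 53 appears nowhere in the plan.

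The stated 43 is not over 80% of either randomised total.

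**Step 2. Does the benchmark include placebo?** 43 > 38 and 43 > 42. It cannot be a liraglutide-only count, either as planned or at the exposure cap. The corrected figure of 46 also exceeds 42.

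**Step 3. The lowest liraglutide completion compatible with the benchmark.** Drug completers = total − placebo completers, with every placebo subject completing. Intervals are exact (Clopper-Pearson).

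| N | Total completers | Drug completers | Percentage | Exact 95% CI |
|---|---|---|---|---|
| 57 | 43 | 43 − 19 = 24 of 38 | 63.2% | 46.0% to 78.2% |
| 57 | 46 | 46 − 19 = 27 of 38 | 71.1% | 54.1% to 84.6% |
| 63 | 43 | 43 − 21 = 22 of 42 | 52.4% | – |
| 63 | 51 | 51 − 21 = 30 of 42 | 71.4% | – |

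With 17 of 19 placebo subjects completing, the first two rows become 26/38 (68.4%) and 29/38 (76.3%). Over 80% of the drug arm itself would be 0.80 × 38 = 30.4, so 31 of 38. The third row shows a further weakness: a fixed count becomes easier to reach when subjects are added because dropout was high.

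**Step 4. How often would this happen?** The plan gives no completion rate by arm, so these are assumptions: placebo completion 95% (range 90% to 100%) and true liraglutide completion 65% or 70%. The total is the sum of two independent binomials (38 and 19).

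| True drug completion | P(total ≥ 43) | P(total ≥ 46) | P(drug arm ≥ 31 of 38) |
|---|---|---|---|
| 65% | 54% (42% to 66%) | 19% (12% to 27%) | 2% |
| 70% | 77% (66% to 86%) | 40% (29% to 52%) | 8% |

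The overall count therefore meets its expectation far more often than the drug arm would meet the same percentage.

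**Step 5. Dose.** No arithmetic is needed. Study Medications lets a subject who fails 1.8 mg continue at 1.2 mg, the titration table (Table 2) allows either dose from Week 2 to Week 54, and footnote 3 allows later changes. No section plans a summary by dose. Even if completion were split by arm, a completer on liraglutide would show only that the flexible regimen was tolerated.

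**The case against.** The case for leaving the plan alone has several parts.

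- **Completion is not the only measure.** The same paragraph also uses adverse events, laboratory results, weight and vital signs, and the action taken on study drug is recorded for each adverse event. This stands. A reader might infer that the trial could not tell whether liraglutide was tolerated at all. The documents do not support that, because these data, grouped by treatment, could show a problem.
- **Pooling is not written as an analysis rule.** The rule that safety is analysed by treatment taken can be read to cover completion. This stands in part. What is certain is that the benchmark counts both arms; that the analysis will do so is an inference. The rule does not separate 1.2 mg from 1.8 mg.
- **There is no pass mark.** The 80% is what the investigators expect. This stands. A reader might infer that a poorly tolerated drug could be formally declared tolerable, but no section sets a threshold for such a declaration.
- **The regimen is flexible by design, and dose is not randomised.** This stands, and completion does capture intolerance of the regimen as a whole. The sentence, however, claims tolerability at the studied doses, in the plural.
- **Dropout for other reasons is already summarised, and it lowers completion.** This stands. It is a reason to separate the causes, not evidence of bias in the drug's favour.
- **Tolerability is not named in the primary objective.** Specific Objectives names efficacy and safety, and the Endpoints paragraph places safety among the secondary outcomes. This stands, so the point should not be presented as a flaw in a primary endpoint.

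**Conclusion.** The concern holds as a mismatch between a stated conclusion and the number meant to support it. The completer count cannot establish tolerability at the studied doses: its benchmark necessarily includes placebo patients, and completion does not distinguish subjects who tolerated 1.8 mg from those who stepped down. The benchmark is also wrong arithmetically, since 43 of 57 is 75.4% and over 80% needs 46.

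On size, 43 completers are compatible with liraglutide completion as low as 63%, and 46 with 71%. Both are limiting cases that assume every placebo subject completes. The probabilities rest on assumed completion rates and illustrate the effect; they are not forecasts.

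The consequence is an unsupported tolerability statement. It is not a false result under a decision rule, because the plan contains no such rule, and it does not leave liraglutide's tolerability unexamined, because other measures are planned.

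**What to change.** Replace the completion sentence in Assessments for Safety with a tolerability summary by arm in the Safety population. Give the number, percentage, exact 95% confidence interval and liraglutide–placebo difference for subjects who:

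1. were on 1.8 mg (drug or vehicle) at Week 54;
2. were on 1.2 mg at Week 54;
3. stopped study drug for an adverse event or intolerance;
4. left for other reasons.

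Add this summary to the list of safety outcomes. Take the Week 54 dose from dispensing and dose-change records, not from the Week 3 determination alone, because later changes are allowed. The last scheduled dispensing is at Week 40, so changes after that visit must be captured too. Keep overall completion as a feasibility figure only. Reconcile 43 with 80% and with the sample size; the dropout allowance, which would leave 51/57 = 89.5%, should be checked at the same time.

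The cost is a wording change and one extra table, with no new visits or patients and no change to treatment. Reasons for withdrawal, dispensing and the Week 3 dose are already recorded. The accountability record as described does not list dose, so confirm that dose and date of change can be recovered. The dose groups will be small. Because dose was not randomised, any comparison of 1.2 mg with 1.8 mg within an arm is descriptive.

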Study Type: This is a phase II, randomized, double-blinded, placebo-controlled clinical trial.

STUDY POPULATION:

Cases: Fifty-seven patients with a diagnosis of idiopathic PD will be recruited and randomized to receive once daily self-administered injections of liraglutide (1.2 or 1.8 mg, as tolerated) or placebo at the same dose range in a 2:1 study design.

Inclusion Criteria:

- Diagnosis of idiopathic PD according to the United Kingdom Parkinson's Disease Society Brain Bank (UKPDSBB) criteria^a for at least 2 years, and/or a DaT-confirmed diagnosis of PD
- Responsive to levodopa or dopaminergic treatment
- Male or female between 25 and 85 years of age at time of enrollment
 - Women of child-bearing potential (WOCBP) must agree to use a reliable method of contraception (e.g., oral contraceptive or long-term injectable or implantable hormonal contraceptive, double barrier methods (such as condom plus diaphragm, condom plus spermicide foam, condom plus sponge), or intra-uterine devices) throughout the duration of the trial period and must have a negative serum pregnancy test at screening
 - Male patients with female partners who have child bearing potential must agree to use adequate contraception throughout the duration of the trial period

- Capacity to give informed consent
- Ability to self-administer, or to arrange a care partner to administer trial drug, to comply with trial protocol, and to attend necessary clinic visits off medication

a: Note: the study team will not consider the UKPDSBB criterion “more than one affected relative” as exclusionary. According to the scientific community, family history is not regarded as exclusionary and this specific criterion is no longer used (reference).

Exclusion Criteria:

- Diagnosis or suspicion of other causes for Parkinsonism, including drug- or toxin-induced parkinsonism and other neurodegenerative conditions, including multiple system atrophy, progressive supranuclear palsy, Huntington's disease, Wilson's disease, or Alzheimer's disease
- Active treatment with anticholinergic medications (e.g., trixyphenidil or tricyclic antidepressants)
- Known abnormality on CT or MRI brain imaging considered to cause symptoms or signs of neurological dysfunction, or considered likely to compromise compliance with trial protocol
- Concurrent dementia defined by a score lower than 120 on the MDRS-2 and/or inability to complete scale per neuropsychologist’s discretion

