The final determination of protocol violations, and therefore the composition of the PP population, will be made prior to unblinding the database and will be documented separately. Analysis of all efficacy

Table 1 (from Aviles-Olmos et al., 2013⁵¹)

Changes in the score on LED, dyskinesia rating scale, Mattis DRS-2, MADRS, and PDQ39 summary index between baseline and month 14

	Baseline	6 months	12 months	Difference, baseline to 12 months	14 months	Difference, baseline to 14 months
	Mean (SD)	Mean (SD)	Mean (SD)	Mean (SD); 95% CI	Mean (SD)	Mean (SD); 95% CI
LED						
Exenatide	973 (454)	1011 (518)	997 (446)	24.3 (123.6); -37, 78	1015 (467)	42.3 (137); -22, 107
Conventional PD medication	977 (493)	1061 (613)	1121 (620)	143.7 (223.6); 49, 238	1125 (638)	148.0 (232); 50, 246
Dyskinesia rating scale, on medication						
Exenatide	2.3 (2.8)	2.5 (4.1)	3.3 (4.5)	1.0 (4.2); -1.0, 3.0	3.2 (4.0)	1.0 (3.8); -0.8, 2.7
Conventional PD medication	2.6 (2.9)	3.5 (3.9)	2.5 (2.7)	-0.04 (2.7); -1.2, 1.1	2.7 (3.5)	0.1 (4.3); -1.7, 1.9
MATTIS DRS-2						
Exenatide	140.1 (7.7)	142.4 (2.3)	142.3 (2.5)	2.2 (6.4); -0.8, 5.2	142.9 (2.0)	2.8 (6.0); -0.1, 5.6
Conventional PD medication	139.5 (4.5)	138.2 (5.1)	136.6 (6.1)	-2.8 (5.3); -0.6, -5.0	135.9 (8.5)	-3.5 (5.8); -1.1, -6.0
MADRS						
Exenatide	10.9 (5.1)	8.6 (4.2)	9.0 (4.5)	-1.9 (4.6); -4.1, 0.3	10.2 (6.7)	-0.7 (5.9); -3.5, 2.1
Conventional PD medication	11.0 (5.4)	11.3 (6.5)	11.4 (5.6)	0.5 (4.5); -1.4, 2.4	12.4 (5.6)	1.5 (4.7); -0.5, 3.4
PDQ39 summary index						
Exenatide	19.2 (13.5)	18.1 (13.4)	19.6 (13.0)	0.4 (11.4); -4.9, 5.7	21.5 (19.6)	2.3 (11.6); -3.1, 7.7
Conventional PD medication	24.5 (12.8)	25.2 (15.8)	24.0 (15.3)	-0.6 (11.2); -5.3, 4.2	23.4 (16.0)	-1.2 (9.1); -5.0, 2.7

variables will be performed on the FAS and PP population. The FAS population will serve as the primary population for the analysis of efficacy data. Analyses based on the PP population will be considered as a sensitivity analysis. Subjects will be analyzed for efficacy according to the treatment to which they were randomized.

All safety outcomes will be analyzed using the Safety population. Subjects will be analyzed for safety according to the treatment they actually received.

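### Does the expected completion of over 80%, given as 43 subjects, need correcting when 57 patients are planned?

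*Combined protocol and SAP*

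**What the plan says.** Assessments for Safety lists the measures of safety and tolerability: vital signs, weight, laboratory values and adverse events. It then adds a completion count: "The number of patients completing the study will be calculated and will establish the tolerability of the study compound at the studied doses". The next sentence gives the expectation: "It is expected that over 80% (43 subjects) will safely complete the study". Neither sentence names a base.

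The planned size appears under Study Population: "Fifty-seven patients with a diagnosis of idiopathic PD will be recruited and randomized". Sample Size Calculation repeats 57, as 38 on liraglutide and 19 on placebo. On attrition, that section says "This sample allows for a 12% dropout of up to 6 subjects" and that the trial would "still maintain 81.3% power with a total of 51 patients". It also provides for extra randomisation if dropout is higher than anticipated, to a ceiling of 63.

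Statistical Methods defines the "Safety population: all randomized subjects who receive at least one dose of study drug". It adds: "Subjects will be analyzed for safety according to the treatment they actually received". The paragraph on descriptive statistics plans a disposition summary with discontinuations and their reasons, an account of everyone screened, and the number and percentage in each analysis population.

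**The concern.** A reader who divides 43 by the only planned total, 57, gets about 75%, not more than 80%. The sentence follows directly on the statement that the completion count will establish tolerability, and it is the only figure the plan offers for judging that count. If it were a criterion, the plan would hold two criteria. Some results would meet the count and miss the percentage, and someone could choose between them after seeing the data.

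The figure also seems to sit badly with the dropout allowance. Exactly 43 completers of 57 would be 14 losses, against the 6 mentioned in Sample Size Calculation.

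**Working it through.** **Inputs.** Count 43 and percentage over 80% (Assessments for Safety). Totals in Sample Size Calculation: 57 planned, 51 after the dropout allowance, 63 as the ceiling.

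**Formulas.** Completion proportion = 43/N. Smallest count strictly above 80% = the whole-number part of 0.80 × N, plus 1.

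| Base N | 43/N | 0.80 × N | Smallest count over 80% |
|---|---|---|---|
| 51 | 84.3% | 40.8 | 41 |
| 57 | 75.4% | 45.6 | 46 |
| 63 | 68.3% | 50.4 | 51 |

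On 57, 45 completers are 78.9% and 46 are 80.7%. The stated 43 is 46 − 43 = 3 too few, so the plan's figure is not reproduced.

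**Which base would fit 43?** 43/0.80 = 53.75, so 43 exceeds 80% only for N of 53 or fewer (43/53 = 81.1%; 43/54 = 79.6%). Neither 53 nor 54 is given as a sample size. On 51 the sentence is literally true, but 51 is the number left after dropout and the text does not name it as the base.

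**Against the dropout allowance.**
- 57 − 6 = 51 completers, which is 89.5% of 57. This is above 80% and also above 43. If both figures are read as floors, neither is contradicted.
- 57 − 43 = 14 losses (24.6%).
- 57 − 46 = 11 losses (19.3%). A floor of 46 therefore also permits more than 6 losses.

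The allowance cannot show which figure is the slip.

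**What uses the figure?**
- Power: the inputs are 38 and 19 patients, a difference of 5.1, standard deviations of 6.4 and 5.3, and a two-sided alpha of 0.05. Neither 43 nor 80% enters.
- Efficacy: comparisons of score changes, with no completion threshold.
- Additional randomisation: triggered by dropout above what was anticipated, with the stated aim of maintaining power. It does not refer to 43 or 80%.
- Safety reviews: the DSMB's material covers retention against its goals, but that section attaches no number to them and does not refer to this sentence.
- Reporting: completers are counted and discontinuations summarised, independently of the expectation.

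**Where the two forms disagree.** With 57 randomised: 43, 44 or 45 completers, which is three possible results. With 63 randomised: 43 to 50, which is eight.

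**The case for a change.** The best case for correcting the sentence is that completion is said to establish tolerability, this is its only numerical yardstick, and a one-sentence repair made before results are known would remove the chance of calling 44 of 57 either met or missed. The arithmetic in that case stands in full. No documented total makes 43 the smallest count above 80%.

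The consequence drawn from it does not stand. The sentence says what is expected. It does not say that the drug is tolerable above the figure and intolerable below it, and tolerability is also judged on the clinical measures listed in the same paragraph. A report of 44 completers would show 44, its denominator and the reasons for stopping, and readers would judge those.

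The argument from dropout is weaker. It reads 80% as a minimum but 43 as an exact forecast. The 6 is the loss the power statement tolerates, not a cap, since the same section plans for higher dropout. The plan also does not define safe completion, which could be narrower than not dropping out, so equating 43 with 14 losses is an assumption.

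**Conclusion.** The sentence is inconsistent with the planned 57: 43 is 75.4%, and more than 80% means at least 46. This rests on taking all 57 randomised patients as the base, which is the natural reading but is not stated. On 51 the figure would be 84.3%.

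It is a clerical inconsistency in a descriptive expectation, and correcting it would alter no analysis, sample size, stopping decision or conclusion. An analyst will report the observed number completing over an explicit denominator, for which the Safety population is already defined, and will present it with the planned disposition summary. The conclusion would differ only if the figure were used as a formal tolerability criterion, and nothing in the documents gives it that role.
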